2.2 STUDY OUTCOMES

Primary Outcomes: The primary outcome for this study is tolerability of medication during treatment. Based on measurements used by other researchers, medication tolerability will be measured via a 0-100 visual analog scale with 0 anchored as “cannot tolerate at all” and 100 as “tolerate perfectly well.” Participants will be asked to estimated tolerability over the previous 2 weeks at each study visit: the primary outcome will be tolerability score at the week 8 visit.

Secondary Outcomes:

- 1) Alcohol reduction measured as a reduction in mean number of grams of pure ethanol consumed per day.
- 2) Treatment discontinuation: defined as patient self-report of stopping medication anytime during the treatment period. Participants will be instructed to notify the study staff in real-time if they discontinue medications, and they will be queried about discontinuation at the week 4 and 8 study visit assessments. Lost-to-follow-up will be assumed to be equivalent to treatment discontinuation.
- 3) Adherence: defined as self-report of the percentage of study medications taken in the past 2 weeks, using a visual analog scale (VAS) from 0 to 100, same as used to assess adherence to HIV medication. Participants will be asked to mark on the ruler what percentage of medication they have taken that week ("0% means no medication, 50% means half your medication, 100% means all your medication"). In addition, medication adherence will be assessed by Riboflavin (50 mg) that will be included in the capsules by the pharmaceutical laboratory. This allows for assessment of medication adherence in both medication arms. Visual inspection of the urine for the presence or absence of riboflavin using ultraviolet (UV) light at the long wave setting (33 nm) in a room with low ambient light will be conducted.
- 4) Reported side effects. We will use a Symptom Checklist based on side effects reported in prior studies of naltrexone, plus an open-ended question to assess for any side effects from study medications in the past 4 weeks at visits 4 and 8. Participants side effects will be rated by trained research assessors, using the Guidelines for Severity Grades (mild, moderate, severe, and life-threatening, death) (See Box 1).
- 5) Medication Satisfaction: This 14-item questionnaire assesses satisfaction with medication to treat chronic conditions and difficulty/inconvenience of use.

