5. ASSESSMENTS

5.1 BASELINE ASSESSMENT

Participants will be assessed as part of this study using validated interview instruments covering the following topics:

- Demographics (marital status, education, employment, individual Income/security, date of birth, spouse HIV status, living situation)
- Alcohol use by the Timeline Followback (TLFB) calendar method with a 30-day assessment
 - Participants will also be provided with a calendar to record daily alcohol use. They will be asked to complete this calendar at home and bring it back to all subsequent study visits. The calendar will be used as an aid by the RA when completing the TLFB with the participant.
- Depressive symptoms through the Center for Epidemiologic Studies Depression Scale (CES-D)
- Anxiety by the Generalized Anxiety Disorder 7-item Scale (GAD-7)
- ART use and adherence, using modified Adult AIDS Clinical Trial Group (AACTG) ART adherence questions
- Co-morbidities by an adapted Veterans Aging Cohort Study patient questionnaire
- HIV symptoms through a validated HIV Symptom Index from the NIAID Adult AIDS Clinical Trials Group
- Prescription and non-prescription medication use
- Brief Pain Inventory using a modified Short Form of the Russian Brief Pain Inventory
- Adjunct treatments of pain
- Drug use by an adapted version of the Risk Behavior Survey
- General health, quality of life, and cognitive function by the Veterans RAND 12-Item Health Survey (VR-12) and the Medical Outcomes Study HIV Health Survey (MOS-HIV)

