5.2 FOLLOW-UP ASSESSMENTS

Content of assessments administered at the 4- and 8-week visits will be subsets of the baseline assessment. Please see table of study questionnaires at the end of this section. Sections not administered at baseline, but administered at follow-up visits include:

- Medication adherence using modified Adult AIDS Clinical Trial Group (AACTG) ART adherence questions
- Medication satisfaction via the Treatment Satisfaction Questionnaire for Medication (TSQM)
- Medication tolerability using modified Adult AIDS Clinical Trial Group (AACTG) ART adherence questions
- Willingness to Continue Medication

5.2.A. MEDICATION VISITS ASSESSMENTS

Medication adherence and symptoms will be assessed at weeks 2 and 6.

	Study Time Point	

Administered Assessment	Baseline	2-week	4-week	6-week	8-week
Demographics	X				
30-day Alcohol Timeline Followback (TLFB)	X		X		X
Depressive Symptoms (CES-D)	X		X		X
Anxiety (GAD-7)	X		X		X
ART Use & Adherence	X		X		X
Co-Morbidities	X		X		X
HIV Symptom Index	X				
Medications	X		X		X
Brief Pain Inventory	X	X	X	X	X
Adjunct Treatments of Pain	X				
Drug Use (modified RBS)	X		X		X
VR-12 Health Survey & MOS HIV	X		X		X
Baseline Symptom Monitoring	X				
Follow-Up Symptom Checklist		X	X	X	X
Medication Adherence		X	X	X	X
Medication Satisfaction (TSQM)			X		X
Medication Tolerability		X	X	X	X
Willingness to Continue Medication					X

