8. STATISTICAL ANALYSIS

This study will use an intent-to-treat analysis that includes all participants according to their randomized assignment. Descriptive statistics will be calculated for variables at baseline and each follow-up time to assess whether there appear to be any differences across treatment arms.

The main focus of this aim is the evaluation of tolerability within each group (naltrexone and nalmefene).

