8.1 PRIMARY ANALYSES

Descriptive statistics and graphic displays of all outcome measures will be generated.

The main focus of this aim is the evaluation of tolerability within each treatment group (naltrexone and nalmefene), thus the analysis set will be all participants who receive at least one dose of their assigned intervention. We will report descriptives such as mean tolerability score at 8 weeks within each treatment group along with 95% confidence intervals (CIs). No formal testing will be conducted in this aim. If the data are skewed, transformations will be performed (e.g., log transformation) or the median will be reported if no appropriate transformation is identified. We anticipate that mean tolerability

scores at 8 weeks will not be lower than 80 (this is based on prior study of low-dose naltrexone which reported tolerability scores of 89 in both intervention and placebo). We will also evaluate: 1) mean number of grams of pure ethanol consumed per day, 2) the percentage in each group that discontinue medication during the 8 week treatment period, 3) the mean % adherence to medications in each group, 4) the percentage of participants who report severe or life threatening side effects, or experience hepatotoxicity during treatment and 5) the percentage who say that they would continue the medication if given the option. Corresponding 95% confidence intervals will be reported for each of the above variables. For binary variables, 95% exact binomial confidence intervals (CIs) will be reported.

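### Section 8.1 does not specify the change from baseline in alcohol intake, or its 95% CI, although section 2.2 defines the outcome as a reduction

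*Combined protocol and SAP*

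**What the plan says.** Section 2.2 lists as the first secondary outcome "Alcohol reduction measured as a reduction in mean number of grams of pure ethanol consumed per day". Section 3.1 uses the same idea: alcohol reduction is among the outcomes evaluated at the end of treatment, and reduction in alcohol use is among the assessments at weeks 4 and 8.

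The measurement supports a change. Section 5.1 specifies "Alcohol use by the Timeline Followback (TLFB) calendar method with a 30-day assessment" at baseline, and the table in section 5.2.A repeats the 30-day TLFB at weeks 4 and 8.

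Section 8.1 is the only place that specifies the alcohol analysis: "We will also evaluate: 1) mean number of grams of pure ethanol consumed per day". It then adds: "Corresponding 95% confidence intervals will be reported for each of the above variables".

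Two general statements also apply. Section 8 says: "Descriptive statistics will be calculated for variables at baseline and each follow-up time to assess whether there appear to be any differences across treatment arms". Section 8.1 opens with: "Descriptive statistics and graphic displays of all outcome measures will be generated".

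**The concern.** The outcome is a change and the listed estimate is a level. An interval around mean grams per day describes how much an arm drinks, not how much its members have cut down. Followed literally, the plan yields no interval for the outcome that section 2.2 defines, although every measurement needed for one is collected.

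The design gives within-person change particular weight. There is no placebo arm and the two arms are not to be formally compared, so change within each arm is the direct estimate of the stated outcome. If 8.1 leaves it unspecified, the analyst must decide after seeing the data which follow-up visit to use, whether to pair the values, and what to do with participants who have no week-8 value.

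**Working it through.** **The plan's own precision figure.** Section 2.7.A gives one, for tolerability: SD 15.1, 7 evaluable per arm, 95% CI length about 22.4. Check: 2 × 1.96 × 15.1 / √7 = 22.37, which agrees. It does not bear on alcohol. The documents give no alcohol SD, expected change or baseline-to-follow-up correlation.

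**Definition against analysis.**

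| Element | Section 2.2 | Section 8.1, item 1 |
|---|---|---|
| Quantity | Reduction in mean g/day | Mean g/day |
| Baseline used | Implied by a reduction | Not mentioned |
| Time point | Not stated here; end of treatment in 3.1 | Not stated |
| 95% CI | – | On the listed variable, i.e. the mean |

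**What the general descriptives add.** Section 8 would put a baseline mean beside each follow-up mean, and their difference is a descriptive estimate of the fall. Two things are missing.

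1. *A valid interval.* The same people are measured twice. With SD s at each time and correlation r, the SD of the within-person change is s√(2(1 − r)). The two separate intervals carry no information on r, so the interval for the change cannot be recovered from them.

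2. *The same people.* Section 2.7.A expects under 15% loss and assumes 7 evaluable per arm, against 8 randomized. Suppose nobody's drinking changes, the 7 who stay average m and the one lost drank x. The baseline mean is (7m + x)/8 = m + (x − m)/8 and the week-8 mean is m. The arm then shows an apparent fall of (x − m)/8 with no change in anyone: one-eighth of the gap between the lost participant and the rest. If x is below m, it is an apparent rise.

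Section 3.3 records that enrollment into arm A stopped on September 18th, 2018, and that arm B continues to N = 8. Arm A's final number is not given. If it is smaller, one loss weighs more.

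**Precision, as illustration only.** Assume n = 7, equal SDs at both times and a range of r. The 95% half-width for a mean level is t(6)/√7 = 0.92 SD. For the paired change it is 0.92 × √(2(1 − r)):

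| Assumed r | Half-width of mean change (SD units) |
|---|---|
| 0 | 1.31 |
| 0.3 | 1.09 |
| 0.5 | 0.92 |
| 0.7 | 0.72 |
| 0.9 | 0.41 |

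The change is estimated more tightly than the level only if r exceeds 0.5, and the documents do not say whether it does. The point does not depend on this: at any r, an interval for the level is not an interval for the reduction.

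**Week-4 recall.** The TLFB looks back 30 days. Section 3.5.A opens the week-4 window at day 21 with target day 28. At target, recall reaches about 30 − 28 = 2 days before treatment; at window opening, about 30 − 21 = 9 days. The week-8 window opens at day 49, so its recall reaches back only to about day 49 − 30 = 19, after treatment began.

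**The case against.** A reader might infer that the plan reports only the level, cannot show a reduction and ignores baseline. The documents do not support that. Section 8 plans summaries at baseline and at each follow-up time, and section 8.1 covers all outcome measures, which by the section 2.2 definition could include the reduction. Item 1 also shares its wording with section 2.2 and may be shorthand for it. This much stands: a fall can be seen descriptively, and the authors may intend to report it. It does not close the gap, because the stated purpose of the section 8 summaries is to look across arms, and the CI promised in 8.1 attaches to the variable as listed.

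A reader might also infer a quantified loss of precision, or that differences between drinkers hide any change in arms this small. Neither can be shown without an alcohol SD or correlation. A natural comparator, an interval treating the two means as independent, has half-width t(12) × √(2/7) = 1.16 SD at n = 7, but the plan proposes no such interval. A paired interval is narrower than that one only if r exceeds about 0.2.

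It is also fair to say that the stakes are limited. This is a 16-person feasibility study without formal testing, and section 2.7.A does not name alcohol in its rule for proceeding to UH3. That lowers the importance but does not remove the mismatch.

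**Conclusion.** The point holds as a gap in specification. Section 2.2 defines a reduction; section 8.1 specifies a mean with its CI and does not specify the change from baseline or an interval for it. Baseline intake enters only through general descriptives, which allow a fall to be read from two arm means, without a valid interval and possibly over different participants.

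The size in grams per day cannot be stated from the documents. The conclusion rests on reading item 1 as written and, for the differing-participants part, on the plan's own expectation of about 7 of 8 evaluable per arm. Importance is low to moderate. Even a correctly estimated change could not be attributed to either drug, because there is no placebo arm.

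**What to change.** In section 8.1, replace item 1 with the within-participant change in mean grams of ethanol per day from the baseline TLFB to week 8, by arm, with a paired 95% CI.

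- **Skewness.** Use a t-based interval by default and keep 8.1's existing provision for a transformation or the median if the changes are skewed. A change can be zero or negative, so a log cannot be applied to the change itself.
- **Missing values.** Show individual baseline and follow-up values for everyone in the analysis set and state how many in each arm lack a week-8 value. Say how this sits with the intention-to-treat statement in section 8, since the change estimate uses only participants with both values.
- **Week 4.** If it is shown, note that its 30-day recall can include pre-treatment days.

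The cost is a few sentences of analysis text, with no new data or visits. The downside is that participants without a week-8 value do not contribute to the change estimate; the individual listing and the count make that visible.

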9. STAFF TRAINING

All study staff will be trained on the study protocol, including administration of study medication, symptom monitoring, cold-pressor testing, and participant assessment prior to initiation of recruitment and enrollment. Training will take place in-person in St. Petersburg and via webinars.

